1.4.7 Phase 3b/4 Study in Patients with Acute Major Bleeding (14-505)	
Baseline characteristics included a mean age of 77 years, 47% female, 87% Caucasian, and median body mass index 27 kg/m². A total of 90 patients (26%) had gastrointestinal or urinary bleeding, 227 patients (64%) had an intracranial hemorrhage, and 35 patients (10%) had other types of bleeding.
 
...
 
Similarly, no clinically significant changes in vital signs and/or physical examination findings have been observed. Finally, no nAbs to FX, FXa, or andexanet have been detected in the study.
	
Baseline characteristics included a mean age of 77 years, 47% female, 87% Caucasian, and median body mass index 27 kg/m². A total of 90 patients (26%) had gastrointestinal or urinary bleeding, 227 patients (64%) had an intracranial hemorrhage, and 35 patients (10%) had other types of bleeding.
 
...
 
Similarly, no clinically significant changes in vital signs and/or physical examination findings have been observed. Finally, no nAbs to FX, FXa, or andexanet have been detected in the study. Twenty patients (5.7%) had confirmed positive results for anti-andexanet antibodies after treatment. The titers were nearly all low values with no neutralizing activity in any patient samples.
	Edited to align with IB and updated details.	NS
2.4 Safety Objectives	To evaluate the overall safety of andexanet.	
 To evaluate the overall safety of andexanet, including AEs, SAEs, vital signs, physical examinations, clinical laboratory measurements, thrombotic events (TEs), 	Added text to clarify which safety parameters will	NS

		mortality, and immunogenicity.	be measured.	
3.1 Overall Study Design and Plan: Description	
The bolus will begin prior to, but not more than 30 minutes before, the start of surgery (i.e., at the first incision; designated as Time 0). It is possible that the bolus or continuous infusion may be ongoing at the start of surgery. Additional andexanet, be it for extended treatment or re-dosing, may be given at the discretion of the Investigator when specific criteria regarding duration of surgery and/or intra-operative complications are met (see Section 6.2).
 
...
 
Prior to surgery, the American Society of Anesthesiologists classification for each patient will be recorded.
	
The bolus will begin must be completed immediately prior to, but not more than 30 minutes before, the start of surgery (i.e., at the first incision; designated as Time 0). It is possible that the bolus or continuous The infusion may be ongoing at should continue from prior to the start of surgery- (initial skin incision) until the end of surgery (close of skin incision). If the end of surgery occurs prior to completion of the initial 2-hour infusion, the infusion should continue into the postoperative period until it is completed (120 minutes). Additional andexanet, be it for extended treatment or re-dosing, may be given at the discretion of the Investigator when specific criteria regarding duration of surgery and/or intra-operative postoperative complications are met (see Section 6.2).
 
...
 
Prior to surgery, the American Society of Anesthesiologists classification for each patient will be recorded.
	Removed sentence because this point is addressed elsewhere in the protocol.	NS
3.4.1 Study Population	
The study will enroll patients between the ages of 18 and 85 who have recently taken an FXa inhibitor (i.e., within 15 hours prior to surgery or if a local anti-fXa activity level obtained within 2 hours prior to consent is > 100 ng/mL [> 0.5 IU/mL for enoxaparin]) and who require urgent surgery for which reversal of anti-fXa activity is judged necessary.
 
Only patients who are in need of surgery that, in the opinion of the Investigator, cannot be delayed by 12 hours are to be enrolled. Procedures that are associated with a low bleeding risk are not eligible.
	
The study will enroll patients between the ages of 18 and 85 years who have recently taken an FXa inhibitor (i.e., within 15 hours prior to start of surgery or if a local anti-fXa activity level obtained within 2 hours prior to consent is > 100 ng/mL [> 0.5 IU/mL for enoxaparin]) and who require urgent surgery for which reversal of anti-fXa activity is judged necessary.
 
Only patients If the time from last dose is unknown or greater than 15 hours, the patient may be enrolled provided a local anti-fXa activity level obtained within 2 hours prior to consent is > 100 ng/mL [> 0.5 IU/mL for enoxaparin]. In such cases the start of surgery must be no greater than 4
	Language added to more accurately detail potential risks.	S

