APPENDIX E. GUIDANCE FOR SUBMISSION OF POTENTIAL THROMBOTIC EVENTS FOR ADJUDICATION

Adjudication criteria for the diagnosis transient ischemic attacks, strokes, myocardial infarctions (MIs), venous thromboembolism, and arterial systemic embolism are provided below.

Transient Ischemic Attack (TIA) is defined as a transient episode of neurological dysfunction caused by focal brain, spinal cord, or retinal ischemia, with signs or symptoms lasting < 24 hours and no evidence of new infarct on neuroimaging if performed. Investigators should consider submitting cases for adjudication if an event meets this definition.

Stroke is defined as an acute episode of neurological dysfunction consistent with a vascular cause. A stroke will be considered to have occurred if there is a rapid onset of signs and/or symptoms of a new persistent neurological deficit consistent with an obstruction to cerebral blood flow with no apparent nonischemic cause (e.g., trauma, tumor, or infection). Signs or symptoms must last at least 24 hours or, for symptom onset less than 24 hours, have neuroimaging evidence of new infarct. Available neuroimaging studies will be considered to support the clinical impression and to determine if there is a demonstrable lesion compatible with an acute stroke. For the diagnosis of stroke, the following criteria must be fulfilled:

- Rapid onset of a focal/global neurologic deficit with at least 1 of the following: change in level of consciousness, hemiplegia, hemiparesis, numbness or sensory loss affecting 1 side of the body, dysphagia/aphasia, hemianopia, amaurosis fugax, or other new neurological signs/symptoms consistent with stroke.
- The duration of a focal/global neurologic deficit is at least 24 hours, OR the neurological deficit results in death, OR there is neuroimaging evidence of a new infarct.
- There is no other readily identifiable non-stroke cause for the clinical presentation (e.g., brain tumor, trauma, infection, hypoglycemia, peripheral lesion).
- Confirmation of the diagnosis by at least 1 of the following: specialist evaluation, or brain imaging procedure (i.e., computed tomography [CT] scan, magnetic resonance imaging [MRI] scan, cerebral vessel angiography).

If the acute neurological signs represent a worsening of a previous (baseline) deficit, the new signs must have either persisted for more than 1 week, or persisted for more than 24 hours and were accompanied by an appropriate new imaging finding.

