Arterial systemic embolism is defined as abrupt vascular insufficiency associated with clinical and other objective evidence of arterial occlusion in the absence of other likely mechanisms. Clinical signs and symptoms must be consistent with embolic arterial occlusion, and there must be clear evidence of abrupt occlusion of a systemic artery, with at least 1 type of supporting evidence, such as surgical report indicating evidence of arterial embolism, pathological specimens related to embolism removal, imaging evidence consistent with arterial embolism, or autopsy report. Investigators should consider submitting potential systemic arterial embolism cases for adjudication if they meet this definition.

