	
comorbidity.
 
5. Existing “Do Not Resuscitate” order or similar advanced directive.
 
6. The patient has a recent history (within 30 days prior to screening) of a diagnosed TE as follows: venous thromboembolism (including deep vein thrombosis, pulmonary embolism, intracardiac thrombus), myocardial infarction (including asymptomatic troponin elevations), disseminated intravascular coagulation, acute traumatic coagulopathy, cerebrovascular accident, transient ischemic attack, unstable angina pectoris hospitalization, or severe peripheral vascular disease.
 
7. Acute decompensated heart failure or cardiogenic shock at the time of screening.
 
8. The patient has severe sepsis or septic or severe hemorrhagic shock at the time of Screening.
 
9. The patient is pregnant or a lactating female.
 
10. The patient has received any of the following drugs or blood products within 7 days of enrollment:
 
 o Vitamin K antagonist (e.g., warfarin). o Dabigatran. o Prothrombin complex concentrate products (e.g., Kcentra®) or recombinant factor VIIa (e.g., NovoSeven®). o Whole blood, plasma fractions. 
Note: Administration of tranexamic acid, platelets or packed red blood cells is not an exclusion criterion.
	
explained.
 
b. The patient has overt bleeding associated with a fall in hemoglobin level by ≥2g/dL, OR, a hemoglobin ≤8 g/dL if no baseline hemoglobin is available.
 
c. The patient has acute bleeding in a critical area or organ, such as pericardial, intracranial, or intraspinal.
 
3. Any surgical procedure requiring cardiopulmonary bypass, an intra-aortic catheter, or the intra-operative intraoperative use of systemic, intravascular, unfractionated heparin.
 
4. Primary procedure for efficacy assessment is a non-surgical interventional procedure (e.g, lumbar puncture, skin biopsy, cardiac catheterization, endoscopic retrograde cholangio-pancreatography).
 
4.5. Expected survival of < 1 month due to comorbidity.
 
5.6. Existing Known “Do Not Resuscitate” order or similar advanced directive.
 
6.7. The patient has a recent history (within 30 days prior to screening) of a diagnosed TE as follows: venous thromboembolism (including deep vein thrombosis, pulmonary embolism, intracardiac thrombus), myocardial infarction (including asymptomatic troponin elevations), disseminated intravascular coagulation, acute traumatic coagulopathy, cerebrovascular accident, transient ischemic attack, unstable angina pectoris hospitalization, or severe peripheral vascular disease.
 
7.8. Acute decompensated heart failure or cardiogenic shock at the time of
		

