3.5. Safety Plan and Monitoring

The study will be conducted in patients who, by virtue of their condition, will typically be hospitalized or will be seen initially in the emergency department. As such, treatment with andexanet and subsequent monitoring will be done in a medical setting. It is expected that patients requiring urgent surgery will remain hospitalized for at least 12 hours, the timeframe for the primary efficacy evaluations. During the first 12-hour period (Study Day 1), AEs, vital signs, physical examinations, and laboratory testing will be performed as indicated in [Appendix A](#) to monitor safety. Survival status will be ascertained on Study Day 30, and cause of death will be recorded. Antibody samples will be taken at baseline and Day 30 to assess immunogenicity against andexanet, FX, FXa, and host-cell proteins (HCPs).

Of the 352 patients, 9.7% of patients with acute major bleeding in ANNEXA-4 experienced protocol-defined, adjudicated TEs that occurred within 30 days of andexanet treatment. While the attributability of these events to andexanet is uncertain, it is significantly possible that they will occur in the current study, given the anticipated enrolled population, for which reversal of anticoagulation may expose the underlying risk of TEs, and andexanet's known effects on coagulation biomarkers such as D-dimer, F1+2, and TFPI. In this study, patients with TEs within 30 days of Screening, those with a history of hypercoagulable states, and those who received procoagulant products within 7 days of Screening will not be eligible for the study due to their much greater risk for TEs in general and following anticoagulation reversal. In this study, TEs will be considered AEs of special interest (AESIs) and will be reported within 24 hours to the Sponsor. Thrombotic events, both suspected and confirmed by adjudication, will be tracked as safety endpoints for the study. To mitigate the risk of TEs, Investigators are encouraged to consider resumption of an anti-thrombotic agent as soon as it is clinically appropriate.

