4.2. Exclusion Criteria

If a patient meets any of the following criteria, he or she is *not* eligible to participate:

1. Surgery predicted to last > 4 hours or for which the risk of clinically meaningful uncontrolled or unmanageable bleeding is low.
2. Acute life-threatening bleeding at the time of Screening.
3. Any surgical procedure requiring cardiopulmonary bypass, an intra-aortic catheter, or the intra-operative use of systemic, intravascular, unfractionated heparin.
4. Expected survival of < 1 month due to comorbidity.
5. Existing “Do Not Resuscitate” order or similar advanced directive.
6. The patient has a recent history (within 30 days prior to Screening) of a diagnosed TE as follows: VTE (including DVT, PE, intracardiac thrombus); myocardial infarction (including asymptomatic troponin elevations); disseminated intravascular coagulation (DIC); acute traumatic coagulopathy; cerebrovascular accident; transient ischemic attack; unstable angina pectoris hospitalization; or severe peripheral vascular disease (see [Appendix B](#) for DIC scoring algorithm).
7. Acute decompensated heart failure or cardiogenic shock at the time of screening (see [Appendix C](#) for cardiogenic shock definition)

8. The patient has severe sepsis or septic or hemorrhagic shock at the time of Screening (see definition in [Appendix C](#)).
9. The patient is pregnant or a lactating female.
10. The patient has received any of the following drugs or blood products within 7 days of enrollment:
 - VKA (e.g., warfarin).
 - Dabigatran.
 - Prothrombin complex concentrate products (PCC, e.g., Kcentra[®]), recombinant factor VIIa (rfVIIa) (e.g., NovoSeven[®]).
 - Whole blood, plasma fractions.
 - Note: Administration of tranexamic acid (TXA), platelets, or packed red blood cells (PRBCs) is not an exclusion criterion.
11. The patient was treated with an investigational drug < 30 days prior to Screening.
12. Prior treatment with andexanet.

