8.2. Thrombotic Events

Patients will be monitored carefully for signs and symptoms of TEs (i.e., strokes, transient ischemic attacks, myocardial infarctions (MIs), DVTs, PEs, arterial systemic embolisms) throughout the course of the study. Should a diagnosis of a TE be considered, it is expected that an appropriate evaluation will be performed (e.g., head computed tomography [CT]/magnetic resonance imaging [MRI], electrocardiogram [ECG]/cardiac enzymes, lower extremity ultrasound, pulmonary vascular imaging). Investigators are requested to consult the guidance listed in [Appendix E](#) when considering whether an event should be considered a TE and therefore be submitted for adjudication. All events submitted for adjudication will be formally considered a suspected TE. Both suspected TEs and TEs confirmed by adjudication will be monitored as safety endpoints.

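### The 30-day thrombosis exclusion does not name arterial systemic embolism, although Section 3.5 says patients with recent thrombotic events are ineligible

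*Protocol*

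**What the plan says.** Three parts of the protocol bear on this.

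The safety plan. Section 3.5 has a sentence that opens "In this study, patients with TEs within 30 days of Screening" and says that these patients, with two other groups, will not be eligible. The reason given is a much raised risk of TEs, both in general and once anticoagulation is reversed. The sentence speaks of TEs as a class.

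The definition of a TE. Section 8.2 spells out the term: "TEs (i.e., strokes, transient ischemic attacks, myocardial infarctions (MIs), DVTs, PEs, arterial systemic embolisms". Appendix E gives adjudication criteria for the same set ("Adjudication criteria for the diagnosis transient ischemic attacks, strokes, myocardial infarctions (MIs), venous thromboembolism, and arterial systemic embolism are provided below") and gives the last of these its own entry: "Arterial systemic embolism is defined as abrupt vascular insufficiency associated with clinical and other objective evidence of arterial occlusion".

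The eligibility rule. The exclusion criterion in Section 4.2 begins "The patient has a recent history (within 30 days prior to Screening) of a diagnosed TE as follows: VTE (including DVT, PE, intracardiac thrombus". It goes on through myocardial infarction, disseminated intravascular coagulation and acute traumatic coagulopathy, and ends "cerebrovascular accident; transient ischemic attack; unstable angina pectoris hospitalization; or severe peripheral vascular disease". The synopsis has the same list. So does the Amendment 1 change table in Appendix G, where only the criterion's number changes, from 6 to 7, and the list again closes with "cerebrovascular accident, transient ischemic attack, unstable angina pectoris hospitalization, or severe peripheral vascular disease".

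**The concern.** Section 3.5 presents the exclusion of recent TEs as a protection against thrombosis after reversal. The criterion that sites apply leaves out one of the event types that the protocol itself calls a TE. The two texts give different answers for the same patient. Section 3.5 says that someone with a recent arterial embolus outside the brain is ineligible, while the list contains nothing that excludes that person on this ground.

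What is at stake is whether a stated safeguard is delivered. Sites, monitors and ethics committees who read Section 3.5 would believe that recent TEs are excluded as a class. A site following the criteria exactly could enrol such a patient without any protocol deviation.

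**Working it through.** No arithmetic applies beyond a count, so the texts are set side by side.

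1. Match each TE type in Section 8.2 to the exclusion list in Section 4.2.

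| TE type in Section 8.2 | Term in the exclusion list | Named? |
|---|---|---|
| Stroke | Cerebrovascular accident | Yes |
| Transient ischemic attack | Transient ischemic attack | Yes |
| Myocardial infarction | Myocardial infarction | Yes |
| Deep vein thrombosis | Under VTE | Yes |
| Pulmonary embolism | Under VTE | Yes |
| Arterial systemic embolism | None | No |

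Five of six are covered. Appendix E groups the two venous types, so on its five categories four are covered and the same one is missing.

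2. Is the list open or closed? The words that introduce it announce an enumeration, and no item refers to other thrombotic or embolic events. It is closed.

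3. Which text governs? Section 10.1.7 (Eligibility Assessment) has the investigator determine eligibility by comparison with the inclusion and exclusion criteria, and states that the sponsor grants no exceptions or waivers. The list decides and the narrative in Section 3.5 does not.

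4. Do other criteria close the gap?
- Procedures requiring cardiopulmonary bypass, an intra-aortic catheter or intra-operative systemic unfractionated heparin are excluded. This removes some operations for an arterial embolus, but not an operation done without them.
- Intracardiac thrombus is listed. It removes patients in whom such a source has been diagnosed.
- Severe peripheral vascular disease is listed. It may catch some limb cases, but it is a different condition from the abrupt occlusion defined in Appendix E.
- Emboli to the brain are caught as cerebrovascular accident or transient ischemic attack.
- Severe sepsis is excluded, and the investigator must judge reversal necessary. Neither is directed at arterial embolism.

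A patient with a recent non-cerebral arterial embolus and none of these features meets no listed exclusion.

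5. Is this superseded text? Sections 3.5, 4.2 and 8.2 can be read in full only in the original protocol of 17 September 2019. Of Amendment 1, the shown part includes Section 10.1.7, Appendix E and the change table. That table repeats the event list unchanged. Its entry for Section 3.5 alters other sentences (resumption of antithrombotic treatment, visit days) and not the eligibility sentence. It has no entry for Section 8.2. The conflict is read directly in the original and inferred for Amendment 1.

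**The case against.** The strongest reply is that Section 3.5 is a narrative summary, worded too broadly, and never an eligibility rule. There is support for this. The same sentence says that patients with a history of hypercoagulable states are ineligible, yet no criterion in the original Section 4.2 says so; Amendment 1 later added one on inherited coagulopathy. The sentence also counts the 7-day procoagulant window from Screening, while Section 4.2 counts it from enrollment. The exclusion list is broader than Section 8.2 in other directions, since it adds unstable angina and disseminated intravascular coagulation. It can be read as a separate screening definition, with Section 8.2 serving only to define what is monitored after treatment.

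Part of this stands. It may be Section 3.5 that is wrong rather than the list, which is why the direction of the correction is left open. It does not remove the conflict. The list describes its own contents as diagnosed TEs, and Section 3.5 is where the protocol explains why such patients are kept out.

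It also stands that the remaining gap is narrow, because the other criteria remove some of the patients concerned.

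A reader might go further and infer that enrolling these patients would inflate the TE safety rate. The documents do not support that. Under Section 9.2.4.7 a preexisting condition is an AE only if it worsens, so an unchanged embolus is not recorded as one. Extension or recurrence after reversal is a genuine post-treatment safety event, which the endpoint ought to count.

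**Conclusion.** The point holds as an internal contradiction with a safety consequence. The exclusion criterion does not deliver what Section 3.5 states for one of the six TE types in Section 8.2, and following the criteria as written could admit a patient whom Section 3.5 says is kept out.

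No numerical size is claimed. The documents do not say how many candidates for urgent surgery have a recent arterial embolus. The 9.7% TE rate from ANNEXA-4 cannot stand in for it: that is the share of patients with acute major bleeding who had a TE within 30 days of treatment, not the share who arrive with one. A reader tempted to convert the gap into a number of patients or a shift in the TE count would be supplying every input by assumption.

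The conclusion rests on two things: that the list is read as closed, which its wording requires, and, for Amendment 1, that text not logged as changed was not changed. It is more than a clerical slip, because it bears on who may receive the drug, but it is readily corrected.

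**What to change.** Reconcile the exclusion criterion, in both Section 4.2 and the synopsis, with Section 3.5, Section 8.2 and Appendix E. There are two consistent outcomes: the list covers every TE type that the protocol defines, or Section 3.5 is narrowed to the events actually listed. Which eligibility rule applies is a clinical decision for the sponsor. First check the full Amendment 1 text of Sections 3.5, 4.2 and 8.2 to confirm that the conflict is still there.

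The drafting cost is a few words in either case, with the ethics review that Section 13.1 requires for any amendment. Extending the list would make some candidates ineligible, in a number that the documents do not allow one to state. Narrowing Section 3.5 would leave enrolment as it is, but the stated safeguard would then be smaller and should be described as such.
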